# 5.3. Storage

EDP-938 and placebo drug product will be stored and shipped in accordance with the EDP 938-201 Pharmacy Manual. Shipments will use an insulated shipper and contain a temperature-monitoring device. Documentation will be maintained at the clinical study site as outlined in the Pharmacy Manual.

# Site staff will maintain adequate records of the receipt and disposition of all study drug shipped to and/or procured by the site for this study.

Site and/or pharmacy records (as appropriate for the site) must include dates, lot numbers, quantities received, quantities dispensed, date and time of preparation (if applicable), date and time of administration at the site (see Section 5.7), and the identification number of each subject who has received each lot of study drug. Subject's weight should also be recorded in the pharmacy records.

Unused study drug must not be discarded or used for any purpose other than for administration to subjects enrolled into this clinical study.

# 5.5. Handling and Disposal

All study drug bottles at the site **and the set of the** 

Enanta Pharmaceuticals, Inc. will provide instructions for the return or destruction of any unused study drug. If Enanta Pharmaceuticals, Inc. authorizes destruction at the study site, the Investigator must ensure that the materials are destroyed in compliance with applicable environmental regulations, institutional policy, and any special instructions provided by Enanta Pharmaceuticals, Inc., and, that the destruction was adequately documented.

# 5.6. Treatment Assignment/Randomization

Subjects will be randomized to a treatment group using an Interactive Web Response System. Subjects will be randomized to the initial EDP-938 or placebo treatment group as shown below:

Part 1, Cohort 1, Age Group 1 and 2 (randomized 2:1)

- of EDP-938 orally QD for 5 days (8 subjects);
- placebo orally QD for 5 days (4 subjects).

The dose for Part 1 Cohort 2 for each age group will be determined based on review of Part 1 Cohort 1 data.

#### Part 2 (randomized 4:1)

EDP-938 orally QD for 5 days: dose to be determined

- Oral EDP-938 QD for 5 days: dose to be determined (16 subjects);
- Oral placebo QD for 5 days: dose to be determined (4 subjects).

The randomization code will be produced by Enanta Pharmaceuticals, Inc. (or designee). The Enanta Pharmaceuticals, Inc. unblinded biostatistician or designee will review and approve the final randomization list.

During the Screening Period, subjects will be identified by a unique screening number. Subjects who have completed screening assessments and are eligible for participation in the study will be randomized before the first dose of study drug (Day 1).

# 5.7. Study Drug Dose and Administration

Complete instructions for dispensing and administering study drug are presented in the Pharmacy Manual.

#### Hospitalized Subjects

Following randomization, subjects will be administered EDP-938 or placebo QD orally

for 5 days at approximately the same time every day

 $(\pm 1 \text{ hour})$  on each of the 4 subsequent days.

If subjects are discharged before Day 5, the subject's caregiver will be instructed to administer EDP-938/placebo to the subjects QD at approximately the same time every day  $(\pm 1 \text{ hour})$  on each of the remaining dosing days. On Day 3 and Day 5, as applicable,

tudy visits should be scheduled close to the time that the subject normally takes the study drug so that dosing can occur at the site when possible.

## 5.7.1. Dispensing of Study Drug

Study drug must be prepared and dispensed by a qualified pharmacist or other authorized site staff with appropriate training.

Dispensed study drug will be provided to subjects' caregivers. Subjects' caregivers will receive instructions on study drug storage (see Section 5.3) and dosing (see Section 5.7).

#### 5.7.2. Treatment Compliance

For non-hospitalized subjects, the subject's caregiver will be instructed to bring all study drug to the site on Day 3, Day 5, or the End-of-Treatment (EOT) visit (for subjects who discontinue study drug). Both accountability and study drug compliance (via syringe counts) will be reviewed at each study site visit as indicated in the SoA (Appendix 1). the site staff will ask the subject's caregiver why any doses were missed, including administration of partial doses, if applicable. Repeated noncompliance of study drug dosing for any subject, despite continued educational efforts, should be discussed by the Investigator with or the Sponsor's Medical Monitor to consider possible discontinuation of the subject from the study.

## 5.8. Prior and Concomitant Medication

The subject's caregiver will be instructed on the use of concomitant medications during the study. All subjects enrolled in the study must not be administered prohibited concomitant medications and therapies through the end-of-study. Details of prior and concomitant medication use will be recorded in the source documentation and the electronic case report form (eCRF) as indicated in the SoA (Appendix 1).

Prior medications administered to the subjects up to 1 month before the first dose of study drug must be recorded at Screening. Only relevant medications and therapies should be recorded if they were discontinued more than 1 month before signing the ICF. All subjects will receive supportive care according to local institution standards and applicable guidelines.

Concomitant medications and therapies are permitted as indicated for the management of study subjects with the exception of the medications and therapies noted in Section 5.9.

# 5.9. Prohibited Medications and Therapies

Systemic antiviral, antifungal, and antimycobacterial therapies are prohibited within 7 days of Screening and for the duration of the study.

The following are also prohibited:

- Systemic medications other than corticosteroids (either chronically [more than 14 days] or within 21 days before randomization and for the duration of the study) that are known to modulate the host's immune response or increase viral shedding, such as immunomodulatory therapies. In Part 2 only: Investigational or approved medication that is intended to prevent or treat RSV infection is prohibited within the following times before the first dose of study drug and for the duration of the study:
  - ribavirin: 35 days,
  - palivizumab: 100 days,
  - nirsevimab: 350 days,
  - other RSV specific monoclonal antibody: 5 half-lives of the specific antibody,
  - RSV vaccines: 12 months.

Note: If after enrollment the initiation of ribavirin is considered medically appropriate, please contact the Medical Monitor.

• Blood products within 6 months of study drug administration and for the duration of the study.

Breastfeeding mothers should also comply with the prohibited medication and therapies list.

# 6. BLINDING AND UNBLINDING

#### 6.1. Blinding

The study will be double-blinded, meaning that the subjects and their caregivers, investigators, and site staff will be blinded to treatment assignment until the completion of the study. All site staff will be blinded to treatment assignment except for the following individuals:

- Unblinded Enanta/ for purpose of generating and monitoring the randomization list;
- Unblinded Enanta representatives not associated with the day-to-day conduct of the study;
- Unblinded Drug Supply Chain personnel for the purpose of monitoring drug supplies;
- Enanta/ Pharmacovigilance Group and Regulatory Affairs representatives when required to satisfy regulatory reporting requirements;
- Bioanalytical laboratory for the purpose of measuring drug concentrations.

## 6.2. Unblinding

At the initiation of the study, the study site will be instructed on the method for breaking the blind. The unblinding method will use the Interactive Web Response System process.

Unblinding of individual subject treatment by the Investigator should be limited to medical emergencies or urgent clinical situations in which knowledge of the subject's study treatment is necessary for clinical management. In situations where the urgency of the case requires immediate action, investigators should use their best judgment, based on the nature and urgency of the clinical situation, and proceed with unblinding. In emergency situations, the decision to unblind resides solely with the Investigator.

For unblinding, if the local		cannot be reached, si	ites at all locations
should call the following 24	4/7 global medical cover	rage hotline:	. The
medical email address is			

Once a subject's treatment assignment has been unblinded for a medical emergency or urgent clinical situation, the **Section** and study coordinator should be notified within 24 hours of unblinding of the treatment. Information relating to unblinding (e.g., the reason, date) should be clearly recorded in the subject's study file. In addition, the Investigator should consider whether the clinical event that prompted unblinding should be considered an SAE, according to the regulatory definitions or criteria for SAEs and, if so, submit an SAE report as described in Section 9.2.

The will also unblind any SAE reports in compliance with regulatory reporting requirements. In addition, Enanta Pharmaceuticals, Inc. may unblind individual subjects at any time for matters relating to safety concerns.

Note: Investigative sites will be provided country-specific toll-free telephone and fax numbers.

# 6.3. Access to Results for Individual Subjects

During the conduct of the study, Investigators, site personnel, and blinded Contract Research Organization/Sponsor staff will not have access to results for individual subjects that could impact clinician assessments, including results for RSV viral load, confirmatory respiratory pathogen panel testing, biomarkers, and PK.

# 7. STUDY CONDUCT AND VISIT SCHEDULE

# 7.1. Study Site Visits

Key aspects of each part of the study (Screening, Treatment Period [Days 1 through 5]), and Follow-up) are summarized below. Assessments are presented in the SoA (Appendix 1).

For study assessments, a subject's hospitalization status (hospitalized or non-hospitalized) will be based on their status on the day of the visit.

Study sites will be responsible for following up with subjects for any missed study site visits. Communication (such as telephone calls, emails, or other electronic communication methods) with parent(s)/subject's caregiver(s) to facilitate compliance with study procedures between outpatient study visits are encouraged. If a subject is unable to attend a study site visit, a home visit by study site personnel/home health staff may be arranged, if feasible.

#### 7.1.1. Screening Period

All study assessments during the Screening Period are detailed in the SoA (Appendix 1).

The subject's legal representative (henceforth referred to as "caregiver") must review and sign an institutional review board (IRB) or ethics committee (EC)-approved ICF and provide authorization to use protected health information (see Section 12.1.3) before the subject undergoes any study-specific procedures. By signing the ICF, the caregiver will indicate that he or she understands the purpose of, and procedures required for, the study and is willing for the subject to participate in the study.

Some procedures performed as part of standard of care before Screening may be used in determining study eligibility, such as RSV diagnostic test or safety laboratory tests (as specified in the SoA) if they are performed within 72 hours before the ICF is signed. If any assessment is

anticipated to fall outside of that window, the Investigator should consult with the

to determine if the subject can proceed. Screening safety laboratory test samples will be sent to the local laboratory for expedited testing.

RSV diagnosis at Screening will be performed using an approved diagnostic assay locally. A nasal swab will be collected.

Subjects who have symptom onset, defined as the estimated onset of the first sign of respiratory infection and which does not exceed 7 days for Part 1 and 5 days for Part 2, before the signing of the ICF by their caregiver and whose swab sample tests positive for RSV will undergo further screening procedures to determine study eligibility.

Subjects will be randomized after all screening activities that allow assessment of inclusion/exclusion criteria have been completed to the satisfaction of the Investigator. Subjects will be randomized 2:1 (Part 1) or 4:1 (Part 2) to EDP-938:placebo.

#### 7.1.2. Treatment Period (Day 1)

All study assessments on Day 1 are detailed in the SoA (Appendix 1).

All subjects (hospitalized and non-hospitalized) should undergo screening assessments, determined whether eligible, and be randomized and dosed within 24 hours of signing consent. If a subject needs to return the next day from Screening to complete Day 1 assessments, vital sign assessments should be repeated predose.

The following assessments must be done between randomization and dosing:

- Parent/Guardian ReSVinet clinical scoring system;
- Parent/Guardian clinical scoring system, in a subset of subjects;
- Clinical evaluation (Section 8.9);
- Vital signs.

Subjects will be administered a dose of EDP-938/placebo on-site. Subjects will be monitored at the site for safety assessments over the first 3 hours postdose. Hospitalized subjects will have ongoing monitoring as a component of standard of care. The subjects' caregivers will also receive instruction on the appropriate storage and transport of study drug (see Section 5.3).

On Day 1, one nasal swab sample will be collected.

The subjects' caregiver will receive an electronic data capture handheld device

to use for the duration of the study. This device will be used to complete the Parent/Guardian ReSVinet clinical scoring system (QD at approximately the same time each day  $\pm 2$  hours) beginning after randomization, prior to dose. The palatability question should be completed postdose. The subject's caregiver will receive instructions on the proper use and care of the eCOA device, and the device should be brought to each study visit. If a caregiver is unable to use the eDiary, a paper diary may be used.

In a subset of subjects, the subject's caregiver will also complete the clinical scoring system on paper after randomization but before the first dose and subsequently twice daily, approximately every 12 hours.

#### 7.1.3. Treatment Period Days 2 to 5

All study assessments during the Treatment Period are detailed in the SoA (Appendix 1).

#### **Hospitalized Subjects**

Subjects will receive EDP-938 or placebo QD at approximately the same time every day  $(\pm 1 \text{ hour})$  on each of the 4 subsequent days after dosing on Day 1. Hospitalization duration will not be extended solely for study purposes. At discharge, the subject's caregiver will be instructed to administer EDP-938 or placebo QD at approximately the same time every day  $(\pm 1 \text{ hour})$  on each of the remaining dosing days. After discharge, subsequent assessments will follow the schedule for non-hospitalized subjects.

Hospitalized subjects who are discharged before Day 3 should return to the study site for Day 3 and Day 5 visits. Subjects who are discharged on or after Day 3 (but before Day 5), should return to the study site for the Day 5 visit.

#### Non-hospitalized Subjects

Subjects' caregiver(s) will be instructed to administer EDP-938 or placebo to subjects QD at approximately the same time every day ( $\pm 1$  hour) on Day 2 and Day 4. On Day 3 and Day 5 (EOT), subjects should be dosed at the clinic. It is recommended that the study visits on Day 3 and Day 5 be scheduled close to the time that the subject normally takes the study drug so that dosing can occur at the site, when possible. If a subject is unable to attend a study site visit, a home visit by study site personnel may be arranged, if feasible.

#### 7.1.4. Follow-up Period (Days 6 to 28)

All study assessments during the Follow-up Period are detailed in the SoA (Appendix 1).

Follow-up visits will occur 4, 9, and 23 days (study Days 9, 14, and 28 [end-of-study; EOS]) after the last dose of study drug for all subjects including those who discontinue treatment early (before completing 5 days of dosing). The eCOA eDiary device should be returned to the site on or before Day 14 (or post-treatment visit 2 [PT2]).

The Day 28 (EOS Visit) is a follow-up visit for post-treatment safety assessments and may be conducted as a telephone call.

Any subject with ongoing AEs/SAEs at the EOS Visit should be followed up until resolution of their AE/SAE or until the Investigator has determined that the event has stabilized as discussed in Section 9.3.

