# 7.3.2. Procedures for Early Discontinuation of Treatment or Early Discontinuation of Study

Subjects who discontinue treatment early (before completing 5 days of dosing) should return to the study site within 24 hours after the last dose of study drug for an EOT visit. Subjects should then return to the site 4 and 9 days (PT1 and PT2 visits) after discontinuation of study drug for post-treatment follow-up visits. A follow-up visit for post-treatment safety assessments also needs to be scheduled (23 days after study drug discontinuation) and may be conducted as a telephone call.

Subjects who discontinue the study early (before Day 28) should return to the study site within 24 hours if possible and no more than 48 hours later to complete the EOS procedures and return eCOA handheld device per the SoA (Appendix 1). Any subject who withdraws with ongoing AEs/SAEs should be followed up until resolution of their AE(s) or until the Investigator has determined that the AE(s) has stabilized.

Site staff will attempt to contact any subject's caregiver who does not return to the site for the EOT or EOS Visit at least 3 times using the caregiver preferred method of communication,

Clinical Study Protocol
EDP 938-201

followed by a letter requiring delivery notification if the 3 attempts were unsuccessful. Any subject who still cannot be reached following those attempts will be considered lost to follow-up. These subjects will be included in the PK and safety analysis as indicated in Section 11.2.

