#### 8.10.2. Parent/Guardian ReSVinet Clinical Scoring System and Palatability Question

During the study, subjects' parent(s)/guardian(s) will assess the severity of RSV-related signs and symptoms and complete the required response in the Parent/Guardian ReSVinet clinical scoring system using a handheld eCOA eDiary. They will also assess the palatability of study drug. A copy of the scoring system and the palatability question is provided in Appendix 3.

The eCOA eDiary will be provided to the parent(s)/guardian(s) on Day 1, and the Investigator/study site personnel will instruct the parent(s)/caregiver(s) on the completion of the eCOA eDiary. The eCOA eDiary should be returned to the study site at the Day 14 visit (or PT2).

On Day 1, the ReSVinet Scoring System assessment should be completed before administration of the first dose of study drug. Subsequently the eCOA eDiary should be completed predose QD each day through Day 14 and at approximately the same time each day  $\pm 2$  hours. The palatability question should be completed as soon as possible after each dose of study drug is administered.

The eCOA eDiary will automatically record the date and time of the eCOA assessments. Entries should be recorded by the caregiver at approximately the same time each day. Whenever possible, the same parent/caregiver should complete the eCOA eDiary and should be the primary caregiver of the child who has sufficient opportunity to notice or observe the signs and symptoms being evaluated in the eCOA eDiary. Study site personnel will review the completion of the parent/caregiver eCOA on a regular basis to ensure that the eCOA eDiary is completed correctly and on schedule to avoid missing or incorrect data. If a caregiver is unable to use the eDiary, a paper diary may be used.

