### 4.5 Analysis Visit Windows

Study day is defined as the number of days from the date of first dose. Day 1 is the date of first dose. For assessments or events after the first dose date, study day is calculated as the date of interest minus first dose date plus 1 day. For assessments/events before the first dose date, study day is calculated as the date of interest minus first dose date.

Analysis visit windows are described in the tables below.

For vital signs, safety laboratory tests, Professional ReSVinet, and RSV RNA quantitation of viral load:

Analysis Visit #	Analysis Visit Label	Target Day	Derivation	Visit Window
1	Day 1	1	Based on nominal visit	
3	Day 3	3	Based on date of assessment	2 to 4*

5	Day 5	5	Based on date of assessment	4 to 6*
9	Day 9	9	Based on date of assessment	8 to 11
14	Day 14	14	Based on date of assessment	12 to 16

\*The visit on Day 4 should be mapped to analysis Visit #3 unless there is an earlier analysis Visit #3.

For eCOA eDiary (Parent/Guardian Resvinet, Palatability Questionnaire), RESOLVE-	For eCOA eDiary	r (Parent/Guardian Re	SVinet, Palatability	Questionnaire),	, RESOLVE-P
--	-----------------	----------------------------------	----------------------	-----------------	-------------

Analysis Visit #	Analysis Visit Label	Target Day	Timepoint* Assessment	Derivation
1	Day 1	1	AM	Study day =1
1	Day 1	1	PM	Study day =1
2	Day 2	2	AM	Study day =2
2	Day 2	2	PM	Study day =2
3	Day 3	3	AM	Study day =3
3	Day 3	3	PM	Study day =3
4	Day 4	4	AM	Study day =4
4	Day 4	4	PM	Study day =4
5	Day 5	5	AM	Study day =5
5	Day 5	5	PM	Study day =5
6	Day 6	6	AM	Study day =6
6	Day 6	6	PM	Study day =6
7	Day 7	7	AM	Study day =7
7	Day 7	7	PM	Study day =7
8	Day 8	8	AM	Study day =8
8	Day 8	8	PM	Study day =8
9	Day 9	9	AM	Study day =9
9	Day 9	9	PM	Study day =9
10	Day 10	10	AM	Study day =10
10	Day 10	10	PM	Study day =10
11	Day 11	11	AM	Study day =11

11	Day 11	11	РМ	Study day =11
12	Day 12	12	AM	Study day =12
12	Day 12	12	РМ	Study day =12
13	Day 13	13	AM	Study day =13
13	Day 13	13	РМ	Study day =13
14	Day 14	14	AM	Study day =14
14	Day 14	14	PM	Study day =14

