 Subjects who discontinue treatment early (before completing 5 days of dosing) should return to the study site within 24 hours following the last dose of study drug for an EOT visit. Follow-up visits will be scheduled 4 days (PT1, Day 9), 9 days (PT2, Day 14), and 23 days (PT3), Day 28 [EOS]) after the last dose of study drug was administered. Assessments should be performed as indicated, respectively for the Day 9 (PT1), Day 14 (PT2), and Day 28 (EOS/PT3) visit. Subjects who discontinue the study early (before Day 28) should return to the study site within 24 hours and no more than 48 hours later to complete the EOS procedures.

 If multiple assessments are scheduled for the same timepoint, it is recommended that noninvasive procedures being done before more invasive procedures, e.g., first complete eCOA (parent/guardian and clinician eCOAs could be concurrent), then ECG, then vital signs/SpO2, then nasal swab and finally blood draw.

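### Follow-up of children who stop treatment early is timed from the last dose but analysed by study day from the first dose, so some scheduled viral-load timepoints are left empty

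*Protocol*

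**What the plan says.** Protocol 7.1.4 states "Follow-up visits will occur 4, 9, and 23 days (study Days 9, 14, and 28 [end-of-study; EOS" and applies this "after the last dose of study drug for all subjects including those who discontinue treatment early". Protocol 7.3.2 repeats the count from the end of dosing: early stoppers "should return to the study site within 24 hours after the last dose of study drug for an EOT visit" and then "return to the site 4 and 9 days (PT1 and PT2 visits) after discontinuation of study drug". Footnote 5 of the Schedule of Assessments (SAP 7.1; also Protocol Appendix 1) carries both labels at once: "Follow-up visits will be scheduled 4 days (PT1, Day 9), 9 days (PT2, Day 14", again counted from the last dose.

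The SAP works differently. Section 4.5 makes the first dose Day 1 and assigns post-baseline viral load by date of assessment. The windows are Day 3 (2 to 4), Day 5 (4 to 6), Day 9 (8 to 11) and Day 14 (12 to 16). Day 4 has its own rule: "The visit on Day 4 should be mapped to analysis Visit #3 unless there is an earlier analysis Visit #3". No rule places an early stopper's PT1 or PT2 swab by visit name, and SAP 4.3 says that missing data are in general not imputed.

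Protocol 8.10.2 asks caregivers to complete the diary through Day 14, but also says "The eCOA eDiary should be returned to the study site at the Day 14 visit (or PT2".

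**The concern.** A child who stops early and attends every visit that the protocol asks for can still have an empty cell at Day 9 or Day 14, because collection and analysis use different clocks. Protocol 7.3.1 lists adverse events and lack of efficacy among the reasons for discontinuation, so the empty cells need not be unrelated to outcome. At stake are the Day 9 and Day 14 summaries, the model contrasts at those days, and the AUC to Day 14. That AUC is extrapolated further for a child whose last swab is early.

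**Working it through.** **Inputs.** Offsets of +4, +9 and +23 days from the last dose (Protocol 7.1.4). Windows and study-day definition (SAP 4.5). Tolerances of ±1 day for PT1 and ±2 days for PT2 (Schedule of Assessments), assumed to move with the visit.

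**Formula.** With the last dose on study Day L, PT1 = L + 4, PT2 = L + 9 and PT3 = L + 23.

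**The plan's own figure.** L = 5 gives 9, 14 and 28, as stated. No other L does.

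**Nominal schedule under the SAP windows**

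| Last dose | PT1 falls on | Window | PT2 falls on | Window | Empty |
|---|---|---|---|---|---|
| Day 1 | Day 5 | Day 5 | Day 10 | Day 9 | Day 14 |
| Day 2 | Day 6 | Day 5 | Day 11 | Day 9 | Day 14 |
| Day 3 | Day 7 | none | Day 12 | Day 14 | Day 9 |
| Day 4 | Day 8 | Day 9 | Day 13 | Day 14 | neither |
| Day 5 | Day 9 | Day 9 | Day 14 | Day 14 | neither |

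There are two separate causes. For Day 1 and Day 2 stops the re-anchoring is responsible: nominally no swab is scheduled late enough. The Day 7 gap matters nominally only for a Day 3 stop.

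**Day 5 cell.** For a Day 1 or Day 2 stop, the PT1 swab, taken four days after the last dose, becomes the Day 5 value. For a Day 3 stop, if the end-of-treatment swab is taken on Day 3, the nominal PT1 on Day 7 leaves Day 5 empty as well. If that swab is taken on Day 4 after an earlier swab in the Day 3 window, Day 5 is filled.

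**With tolerances.** There are 3 × 5 = 15 combinations of PT1 and PT2 dates. The table counts those that fill both Day 9 and Day 14.

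| Last dose | Day 9 window 8-11 | Day 9 window 7-11 |
|---|---|---|
| Day 1 | 0 of 15 | 0 of 15 |
| Day 2 | 0 of 15 | 2 of 15 |
| Day 3 | 3 of 15 | 6 of 15 |
| Day 4 | 8 of 15 | 12 of 15 |
| Day 5 | 15 of 15 | 15 of 15 |

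For a Day 1 stop, PT2 can fall on Days 8 to 12. It fills Day 9 or, on Day 12, Day 14, but PT1 (Days 4 to 6) never reaches the Day 9 window. These are counts of possible dates, not probabilities. Visits timed from the first dose behave like the last row: PT1 on Days 8 to 10 and PT2 on Days 12 to 16 always fall in their windows.

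**AUC scaling.** SAP 4.13.2 multiplies the AUC by 14/t_last, with time counted from the first dose, so t_last = study day − 1 in nominal days.
- Day 1 stop: 14/9 = 1.56.
- Day 2 stop: 14/10 = 1.40.
- Day 3 stop: 14/11 = 1.27.
- Day 4 stop: 14/12 = 1.17.
- Completer: 14/13 = 1.08.

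The scaling carries the average load of the observed stretch over the unobserved days. If load is still falling, that overstates the 14-day value.

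**The case against.** **The primary endpoint stops before these days.** It covers baseline through the treatment phase, so empty Day 9 and Day 14 cells remove nothing from it directly. This stands. The one route to the treatment phase is the Day 3 stop with its end-of-treatment swab on Day 3. A PT1 swab standing as Day 5 is not in itself an error, since an off-drug Day 5 value can be a legitimate value.

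**The children are not lost.** A reader might infer that they drop out of the treatment comparison. The documents do not support that. The AUC needs only two points and uses actual times. The mixed model in SAP 4.13.5 keeps children with partial visits. Time to undetectable is defined by dates and samples rather than windows, so a Day 7 swab still counts there. What is empty is a visit cell.

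**The tolerances soften the mapping.** Also true: Day 3 and Day 4 stops may or may not fill both cells. Only the result for Day 1 and Day 2 stops is certain.

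**A late Visit 5.** A reader might add that a Visit 5 on Day 7 is lost too. Its tolerance is Day 5 ±1, which matches the 4-6 window, so that would be an off-schedule visit and not a fault of the plan.

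**The diary.** A reader might infer that caregiver scores necessarily end at PT2, nominally on Days 10 to 13 for early stoppers. The wording is only ambiguous, because completion through Day 14 is also required. RESOLVE-P is kept on paper, so returning the device does not end it.

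**Who can be helped.** Children who leave the study altogether have an end-of-study visit without a swab, or no further data if consent is withdrawn. No re-timing recovers those.

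**Conclusion.** The point holds as a conflict of anchors plus a one-day gap in the windows. The protocol gives early stoppers two incompatible visit dates, and the SAP analyses on a clock that matches the protocol's follow-up dates only for a last dose on Day 5. On the nominal schedule, three of the four possible early-stop days leave a scheduled viral timepoint empty. For Day 1 and Day 2 stops, no dates within tolerance fill both Day 9 and Day 14.

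The consequence is mainly secondary: Day 9 and Day 14 summaries and model contrasts, and a Day 14 AUC scaled by 1.40 to 1.56 rather than 1.08. The number of children cannot be computed, because the documents give no discontinuation rate, and no direction of bias between arms is shown. The result assumes that tolerances move with the visit, that no unscheduled swab is taken, and that windows are applied by date as SAP 4.5 states.

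**What to change.** 1. **SAP 4.5.** Widen the Day 9 window from 8-11 to 7-11. Where two swabs fall in it, use the one closest to Day 9 and, if tied, the later. The tie rule is needed: a Day 2 stop with PT1 on Day 7 and PT2 on Day 11 has two swabs, each two days from Day 9. This rescues the nominal Day 3 stop but does nothing for nominal Day 1 and Day 2 stops.
2. **Protocol 7.1.4, 7.3.2 and footnote 5 of the Schedule of Assessments.** For early stoppers who remain in the study, schedule the nasal swab and Professional ReSVinet on study Days 5, 9 and 14 counted from the first dose. Continue the caregiver diary through study Day 14 before the device is returned.
3. **Safety follow-up visits.** Reconcile the conflicting anchors in these passages. Which anchor applies is for the sponsor to decide.

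**Cost.** The first change is one table cell and one sentence, and under Protocol 11.2 it must be made before unblinding. A Day 7 swab would carry the label Day 9, which matters little for the AUC because it uses actual times. The second needs a short amendment. If safety visits stay on the last-dose anchor, a few visits may be added. A Day 3 stop, for example, would have nominal Days 7 and 12 for safety and Days 5, 9 and 14 for efficacy. The tolerances would allow Days 7 and 9 to be combined on Day 8, and Days 12 and 14 on one visit from Day 12 to Day 14.
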